## **7.2 Study completion and post-study treatment**

Each subject will be required to complete the study in its entirety and thereafter no further study treatment will be made available to them. Study completion is defined as when the last subject completes their End of Study visit, and any repeat assessments associated with this visit have been documented and followed-up appropriately by the Investigator, or in the event of an early study termination decision, the date of that decision.

At a minimum, subjects will be contacted for safety evaluations during the 30 days following the Study Completion visit, including a final post-study safety contact at the 30-day point. Documentation of attempts to contact the subject should be recorded in the source documentation.

### **7.2.1 Lost to follow-up**

For subjects whose status is unclear because they fail to appear for study visits without stating an intention to discontinue or withdraw, the investigator should show "due diligence" by documenting in the source documents steps taken to contact the subject, e.g. dates of telephone calls, registered letters, etc. A subject should not be formally considered lost to follow-up until his/her scheduled end of study visit would have occurred.

## **7.3 Withdrawal of consent**

Patients may voluntarily withdraw consent to participate in the study for any reason at any time.

Withdrawal of consent occurs only when a patient does not want to participate in the study anymore **and** does not want any further visits or assessments **and** does not want any further study related contact **and** does not allow analysis of already obtained biologic material.

If a patient withdraws consent, the investigator must make every effort to determine the primary reason for this decision and record this information. Study treatment must be discontinued and no further assessments conducted. All biological material that has not been analyzed at the time of withdrawal must not be used. Further attempts to contact the patient are not allowed unless safety findings require communicating or follow-up.

## **7.4 Study Stopping rules**

The study will be stopped if any of the following criteria are met and no further dosing will be taken pending a full safety review:

- 2 severe AEs are reported
- 3 subjects experience a persistent (> 24 hours) and reproducible increase in serum creatinine >0.3 mg/dL from baseline
- 3 or more subjects experience a similar AE which is assessed as either moderate or severe in intensity

## **7.5 Early study termination**

The study can be terminated at any time for any reason by Novartis. Should this be necessary, subjects should be seen as soon as possible and treated as a prematurely withdrawn subject. The investigator may be informed of additional procedures to be followed in order to ensure that adequate consideration is given to the protection of the subject's interests.

The investigator will be responsible for informing IRBs/IECs of the early termination of the trial.

## 8 Procedures and assessments

**Table 8-1 Assessment schedule**

Subjects should be seen for all visits on the designated day, with the assessments performed as per schedule, within the allowed “visit/assessment window” specified in the Site Operations Manual.

Study Phase	Screening	PBO Run In	Baseline				Treatment							Study Completion							
			V1	V2 	V3 	V4	V5	V6 	V7	V8	V9	V10	V11								
Visit Numbers 	V1	V2 	-17 to -3	-2	-1		1	3	7	14	21	27		28		35					
Study Day(s)	-42 to -18	(-2, +1)	(-2, 0)	(-2, 0)				(-1, +1)	(-1, +1)	(-1, +2)	(-1, +1)	(-2, +1)		(-1, +1)		(-2, +2)					
Time (post-dose)	-	-	-	0h	4h 	8h 	12h 	0h	-	-	-	-	-	0h	1h	2h	3h	4h 	8h 	12h 	-
Informed consent	X																				
Inclusion / Exclusion criteria 	X			X																	
Medical history/current medical conditions	X																				
Demography	X																				
Hepatitis and HIV Screen 	X																				
Blood pressure / Pulse rate 	X	X	X	X				X	X	X	X	X	X				X				
Body temperature	X		X	X																	
Body Height and Weight	X																				
Ambulatory blood pressure monitoring  	X 		X										X 		X 						
Physical examination 	X	X						X					X		X				X		
Alcohol Test, Drug Screen, and Cotinine Test 	X																				
ECG evaluation	X												X								
Routine Clinical Laboratory Tests 	X		X										X	X	X				X		
Urinalysis	X		X										X	X	X				X		
Suicidality Assessment with C-SSRS	X		X										X			X			X		
IVRS 	X					X															
Patient diary 		X	X										X								
Dose administration		X	X		X								X								
Concomitant therapies													as required						as required		
Adverse events													as required						as required		
Serious adverse events													as required						as required		
Comments													as required						as required		
Corporate Confidential Information				X									X	X	X	X	X	X			
				X	X	X	X	X					X			X	X	X			
				X	X	X										X		X			
					X		X									X					
Study completion information																		X			

Visit structure given for internal programming purpose only

## Corporate Confidential Information

Urine pooling periods are 0-4 hr and 4-8 hr.

Day-1, 12 h PD blood collection is optional

Day 28, 12 h PK and PD collection is optional

Captured in source documentation only

Standing and sitting vitals will be taken at screening; on subsequent visits, readings will be taken in a sitting position (standing may be performed if necessary at Investigator discretion)

Documented ABPM values within 3 months of screening is acceptable for inclusion into the trial

## Corporate Confidential Information

Routine clinical laboratory tests includes hematology, clinical chemistry (+ lipid profile), and NTproBNP

ABPM assessments during the treatment period must be recorded by unblinded site personnel

IVRS must be used to register a patient at screening, and to randomize a patient prior to the first dose once eligibility is confirmed

Patient diary will be reviewed at V3 (to assess adherence to medication regimen during the PBO run-in), and at every visit during the treatment period

ABPM readings will be obtained over a 24 h period. Patients must return to the site after 24 h to have the device removed and results transmitted by site personnel.

Visitwindows allow V3 to overlap with V2 and V4; note that no visits can be combined together

Visit is optional

## **8.1 Informed consent procedures**

Eligible patients may only be included in the study after providing written (witnessed, where required by law or regulation), IRB/IEC-approved informed consent.

Informed consent must be obtained before conducting any study-specific procedures (i.e. all of the procedures described in the protocol). The process of obtaining informed consent should be documented in the subject source documents.

The date of signing of informed consent (and withdrawal, if later withdrawn) should be documented in the CRF.

Novartis will provide to investigators a proposed informed consent form that complies with the ICH GCP guideline and regulatory requirements and is considered appropriate for this study. Any changes to the proposed consent form suggested by the investigator must be agreed to by Novartis before submission to the IRB/IEC.

Pregnancy outcomes must be collected for the female partners of any males who took study treatment in this study. Consent to report information regarding these pregnancy outcomes should be obtained from the mother.

### **Corporate Confidential Information**

In the event that Novartis wants to perform testing on the samples that are not described in this protocol, additional Institutional Review Board and/or Ethics Committee approval will be obtained.

A copy of the approved version of all consent forms must be provided to the Novartis monitor after IRB/IEC approval.

## **8.2 Subject demographics/other baseline characteristics**

Subject demographic and baseline characteristic data will be collected on all subjects.

Relevant medical history/current medical conditions data includes data until signature of informed consent. Where possible, diagnoses and not symptoms will be recorded.

Investigators have the discretion to record abnormal test findings on the medical history CRF whenever in their judgment, the test abnormality occurred prior to the informed consent signature.

## 8.3 Efficacy / Pharmacodynamics

Pharmacodynamic assessments are specified below, with the methods for assessment and recording specified in the Study Operations Manual. Assessments will be performed/samples collected at the timepoint(s) defined in the [Assessment schedule](#).

In order to better define the PD profile, the timing of the sample collection may be altered based on emergent data. The number of samples/blood draws and total blood volume collected will not exceed those stated in the protocol. The results need to remain blinded during the study.

### 8.3.1 Ambulatory blood pressure monitoring

Continuous blood pressure monitoring will be performed over 24 hour periods to assess blood pressure, heart rate, mean arterial pressure, and pulse pressure.

The ABPM device vendor will provide a reference/user manual giving more specific details on patient considerations for inclusion. Procedures for set-up, validation, quality control, use of software and transfer of data, and guidance for performing the measurements will also be provided in the vendor manual. Investigator site staff that will be performing the ABPM measurements will be trained appropriately by the device vendor to ensure the devices are used in the correct manner. Training will occur prior to initial use of the devices.

## 8.4 Safety

Safety assessments are specified below; methods for assessment and recording are specified in the Site Operations Manual, with the [Assessment schedule](#) detailing when each assessment is to be performed.

### 8.4.1 Physical examination

A complete physical examination will include the examination of general appearance, skin, neck (including thyroid), eyes, ears, nose, throat, lungs, heart, abdomen, back, lymph nodes, extremities, vascular and neurological. If indicated based on medical history and/or symptoms, rectal, external genitalia, breast, and/or pelvic exams may be performed.

Information for all physical examinations should be included in the source documents and will not be transferred to the sponsor as part of the study analysis. Significant findings that are present prior to informed consent are included in the Relevant Medical History section of the source documents. Significant findings observed after informed consent signature which meet the definition of an Adverse Event must be appropriately recorded on the Adverse Event eCRF section.

### 8.4.2 Vital signs

- Body temperature
- Blood pressure (BP)
- Pulse

#### **8.4.3 Height and weight**

- Height
- Body weight
- Body mass index (BMI) will be calculated (Body weight (kg) / [Height (m)])

#### **8.4.4 Laboratory evaluations**

Clinically relevant deviations of laboratory test results occurring during or at completion of the study must be reported and discussed with Novartis personnel. The results should be evaluated for criteria defining an adverse event and reported as such if the criteria are met. Repeated evaluations are mandatory until normalization of the result(s) or until the change is no longer clinically relevant. In case of doubt, Novartis personnel should again be contacted.

#### **Hematology**

Hemoglobin, hematocrit, red blood cell count, white blood cell count with differential and platelet count will be measured.

#### **Clinical chemistry**

Sodium, potassium, creatinine, urea, uric acid, chloride, albumin, calcium, alkaline phosphatase, total bilirubin, LDH, GGT, AST, ALT, glucose, total cholesterol, creatine kinase (CK), and triglycerides.

If the total bilirubin concentration is increased above 1.5 times the upper limit of normal, direct and indirect reacting bilirubin should be differentiated.

#### **Corporate Confidential Information**

#### **Urinalysis**

Urine test by dipstick e.g. Combur9: leucocytes, nitrite, pH, protein, glucose, ketones, urobilinogen, bilirubin, blood/ hemoglobin

If the dipstick result is positive for protein, nitrite, leucocytes and/or blood, the sample will be sent for microscopic analysis of WBC, RBC and casts.

#### **8.4.5 Electrocardiogram (ECG)**

Each ECG tracing should be labeled with study number, subject initials, subject number, date and time, be appropriately signed and dated to confirm review and filed in the study site source documents. For any ECGs with subject safety concerns, two additional ECGs should be performed to confirm the safety finding. Clinically significant ECG findings prior to dosing with investigational treatment must be discussed with the sponsor.

Full details of all procedures relating to the ECG collection and reporting will be contained in the technical manual which is provided to the site by the core laboratory.

**For all studies:**

PR interval, QRS duration, heart rate, RR, QT, QTc

The Fridericia QT correction formula (QTcF) should be used for clinical decisions.

**8.5 Pharmacokinetics**

PK samples will be collected at the time-points defined in the [Assessment schedule](#).

Further details on sample collection, numbering, processing and shipment can be found in the Site Operations Manual.

Corporate Confidential Information

For standard pharmacokinetic abbreviations and definitions see the list provided at the beginning of this protocol.

The following pharmacokinetic parameters will be determined using the actual recorded sampling times and non-compartmental method(s) with Phoenix WinNonlin (Version 6.2 or higher): Cmax, Tmax, AUClast, AUC0-t from the plasma concentration-time data. Other pharmacokinetic parameters may be determined, if relevant.

**8.6 Other assessments**

Corporate Confidential Information

---

## Corporate Confidential Information

## **9 Safety monitoring**

### **9.1 Adverse events**

An adverse event (AE) is any untoward medical occurrence (i.e., any unfavorable and unintended sign [including abnormal laboratory findings], symptom or disease) in a patient or clinical investigation subject *after providing written informed consent* for participation in the study. Therefore, an AE may or may not be temporally or causally associated with the use of a medicinal (investigational) product.

The occurrence of adverse events should be sought by non-directive questioning of the subject at each visit during the study. Adverse events also may be detected when they are volunteered by the subject during or between visits or through physical examination, laboratory test, or other assessments.

Abnormal laboratory values or test results constitute adverse events only if they fulfill at least one of the following criteria:

- they induce clinical signs or symptoms,
- they are considered clinically significant,
- they require therapy.

Clinically significant abnormal laboratory values or test results should be identified through a review of values outside of normal ranges/clinically notable ranges, significant changes from baseline or the previous visit, or values which are considered to be non-typical in patients with underlying disease. Investigators have the responsibility for managing the safety of individual subject and identifying adverse events. Alert ranges for liver related events are included in [Section 9.3](#).

Adverse events must be recorded on the Adverse Events CRF for subjects that pass screening and enter into the study. The adverse events should be reported according to the signs, symptoms or diagnosis associated with them, and accompanied by the following information:

1. the severity grade
  - mild: usually transient in nature and generally not interfering with normal activities
  - moderate: sufficiently discomforting to interfere with normal activities
  - severe: prevents normal activities
2. its relationship to the investigational treatment (no/yes), or other study treatment (non-investigational) (no/yes), or both or indistinguishable,
3. its duration (start and end dates) or if the event is ongoing an outcome of not recovered/not resolved should be reported.
4. whether it constitutes a serious adverse event (SAE). See [Section 9.2](#) for definition of SAE
5. action taken regarding [study/investigational] treatment(select as appropriate).

All adverse events should be treated appropriately. Treatment may include one or more of the following:

- no action taken (i.e. further observation only)
- study treatment dosage adjusted/temporarily interrupted
- study treatment permanently discontinued due to this adverse event
- concomitant medication given
- non-drug therapy given
- subject hospitalized/subject's hospitalization prolonged

6. its outcome (continuing at final exam; resolved)

Once an adverse event is detected, it should be followed until its resolution or until it is judged to be permanent, and assessment should be made at each visit (or more frequently, if necessary) of any changes in severity, the suspected relationship to the study drug, the interventions required to treat it, and the outcome.

Information about common side effects already known about the investigational drug can be found in the Investigator Brochure (IB) or Core Data Sheet (for marketed drugs) or will be communicated between IB updates in the form of Investigator Notifications. This information will be included in the subject informed consent and should be discussed with the subject during the study as needed.

The investigator should also instruct each subject to report any new adverse event (beyond the protocol observation period) that the subject, or the subject's personal physician, believes might reasonably be related to study treatment. This information should be recorded in the investigator's source documents, however, if the AE meets the criteria of an SAE, it must be reported to Novartis.

## **9.2 Serious adverse event reporting**

### **9.2.1 Definition of SAE**

An SAE is defined as any adverse event (appearance of (or worsening of any pre-existing) undesirable sign(s), symptom(s) or medical conditions(s) which meets any one of the following criteria:

- is fatal or life-threatening
- results in persistent or significant disability/incapacity
- constitutes a congenital anomaly/birth defect
- requires inpatient hospitalization or prolongation of existing hospitalization, unless hospitalization is for:
  - Routine treatment or monitoring of the studied indication, not associated with any deterioration in condition
  - elective or pre-planned treatment for a pre-existing condition that is unrelated to the indication under study and has not worsened since the start of study drug
  - treatment on an emergency outpatient basis for an event not fulfilling any of the definitions of a SAE given above and not resulting in hospital admission
  - social reasons and respite care in the absence of any deterioration in the patient's general condition
- is medically significant, i.e. defined as an event that jeopardizes the subject or may require medical or surgical intervention.

Life-threatening in the context of a SAE refers to a reaction in which the subject was at risk of death at the time of the reaction; it does not refer to a reaction that hypothetically might have caused death if more severe.

All malignant neoplasms will be assessed as serious under "medically significant" if other seriousness criteria are not met.

Any suspected transmission via a medicinal product of an infectious agent is also considered a serious adverse reaction.

Medical and scientific judgment should be exercised in deciding whether other situations should be considered serious reactions, such as important medical events that might not be immediately life threatening or result in death or hospitalization but might jeopardize the patient or might require intervention to prevent one of the other outcomes listed above. Examples of such events are intensive treatment in an emergency room or at home for allergic bronchospasm, blood dyscrasias or convulsions that do not result in hospitalization or development of dependency or abuse.

All AEs (serious and non-serious) are captured on the CRF, SAEs also require individual reporting to DS&E as per [Section 9.2.2](#).

### **9.2.2 SAE reporting**

To ensure subject safety, every SAE, regardless of causality, occurring after the subject has provided informed consent and until 30 days after the last study visit must be reported to Novartis within 24 hours of learning of its occurrence as described below. Any SAEs experienced after this should only be reported to Novartis if the investigator suspects a causal relationship to study treatment.

Recurrent episodes, complications, or progression of the initial SAE must be reported as follow-up to the original episode, regardless of when the event occurs. This report must be submitted within 24 hours of the investigator receiving the follow-up information. An SAE that is considered completely unrelated to a previously reported one should be reported separately as a new event.

SAEs (initial and follow-up) that are recorded electronically in the Electronic Data Capture system should be entered, saved and e-signed within 24 hours of awareness of the SAE or changes to an existing SAE. These data will automatically be submitted to Novartis Drug Safety & Epidemiology immediately after investigator signature or 24 hours after entry, whichever occurs first. Study site personnel must also inform the Clinical Trial Leader.

Follow-up information provided should describe whether the event has resolved or continues, if and how it was treated, whether the treatment code was broken or not and whether the subject continued or withdrew from study participation. Each re-occurrence, complication, or progression of the original event should be reported as a follow-up to that event regardless of when it occurs.

If the SAE is not previously documented in the Investigator's Brochure or Package Insert (new occurrence) and is thought to be related to the investigational treatment a Drug Safety and Epidemiology Department associate may urgently require further information from the investigator for Health Authority reporting. Novartis may need to issue an Investigator Notification (IN) to inform all investigators involved in any study with the same investigational treatment that this SAE has been reported. Suspected Unexpected Serious Adverse Reactions (SUSARs) will be collected and reported to the competent authorities and relevant ethics committees in accordance with EU Guidance 2011/C 172/01 or as per national regulatory requirements in participating countries.

### **9.3 Liver safety monitoring**

To ensure subject safety and enhance reliability in determining the hepatotoxic potential of an investigational drug, a standardized process for identification, monitoring and evaluation of liver events has to be followed.

The following two categories of abnormalities / adverse events have to be considered during the course of the study:

- Liver laboratory triggers, which will require repeated assessments of the abnormal laboratory parameter
- Liver events, which will require close observation, follow-up monitoring and completion of the standard base liver CRF pages

Please refer to [Table 9-1](#) and [Table 9-2](#) for complete definitions of liver laboratory triggers and liver events.

Every liver laboratory trigger or liver event should be followed up by the investigator or designated personal at the trial site, as summarized below and detailed in [Table 9-2](#).

#### **For the liver laboratory trigger:**

- Repeating the LFT within the next week to confirm elevation.

These LFT repeats should be performed using the central laboratory if possible. If this is not possible, then the repeats can be performed at a local laboratory to monitor the safety of the patient. Repeats laboratory should then be performed at central laboratory as soon as possible. If a liver event is subsequently reported, any local LFTs previously conducted that are associated with this event should be reported on the Liver CRF pages.

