**Table 9-1 Liver Event and Laboratory Trigger Definitions**

Definition/ threshold	
Liver laboratory triggers	
 
• <math>3 \times \text{ULN} < \text{ALT} / \text{AST} \leq 5 \times \text{ULN}</math>
 
• <math>1.5 \times \text{ULN} < \text{TBL} \leq 2 \times \text{ULN}</math>
 

Liver events	
 
• <math>\text{ALT or AST} > 5 \times \text{ULN}</math>
 
• <math>\text{ALP} > 2 \times \text{ULN}</math> (in the absence of known bone pathology)
 
• <math>\text{TBL} > 2 \times \text{ULN}</math> (in the absence of known Gilbert syndrome)
 
• <math>\text{ALT or AST} > 3 \times \text{ULN}</math> and <math>\text{INR} > 1.5</math>
 
• Potential Hy's Law cases (defined as <math>\text{ALT or AST} > 3 \times \text{ULN}</math> and <math>\text{TBL} > 2 \times \text{ULN}</math> [mainly conjugated fraction] without notable increase in <math>\text{ALP}</math> to <math>> 2 \times \text{ULN}</math>)
 
• Any clinical event of jaundice (or equivalent term)
 
• <math>\text{ALT or AST} > 3 \times \text{ULN}</math> accompanied by (general) malaise, fatigue, abdominal pain, nausea, or vomiting, or rash with eosinophilia
 
• Any adverse event potentially indicative of a liver toxicity *
 

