**Table 9-2 Follow Up Requirements for Liver Events and Laboratory Triggers**

Criteria	Actions required	Follow-up monitoring
Potential Hy's Law case a	
 
• Discontinue the study drug immediately
 
• Hospitalize, if clinically appropriate
 
• Establish causality
 
• Complete liver CRF
 
	ALT, AST, TBL, Alb, PT/INR, ALP and $\gamma$ GT until resolution c (frequency at investigator discretion)
ALT or AST		
$> 8 \times \text{ULN}$	
 
• Discontinue the study drug immediately
 
• Hospitalize if clinically appropriate
 
• Establish causality
 
• Complete liver CRF
 
	ALT, AST, TBL, Alb, PT/INR, ALP and $\gamma$ GT until resolution c (frequency at investigator discretion)
$> 3 \times \text{ULN}$ and $\text{INR} > 1.5$	
 
• Discontinue the study drug immediately
 
• Hospitalize, if clinically appropriate
 
• Establish causality
 
• Complete liver CRF
 
	ALT, AST, TBL, Alb, PT/INR, ALP and $\gamma$ GT until resolution c (frequency at investigator discretion)
$> 5$ to $\leq 8 \times \text{ULN}$	
 
• Repeat LFT within 48 hours
 
• If elevation persists, continue follow-up monitoring
 
• If elevation persists for more than 2 weeks, discontinue the study drug
 
• Establish causality
 
• Complete liver CRF
 
	ALT, AST, TBL, Alb, PT/INR, ALP and $\gamma$ GT until resolution c (frequency at investigator discretion)

Criteria	Actions required	Follow-up monitoring
> 3 × ULN accompanied by symptoms b	
 
Discontinue the study drug immediately
 
Hospitalize if clinically appropriate
 
Establish causality
 
Complete liver CRF
 
	ALT, AST, TBL, Alb, PT/INR, ALP and γGT until resolution c (frequency at investigator discretion)
> 3 to ≤ 5 × ULN (patient is asymptomatic)	
 
Repeat LFT within the next week
 
If elevation is confirmed, initiate close observation of the patient
 
	Investigator discretion Monitor LFT within 1 to 4 weeks
ALP (isolated)		

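### No visible step orders PT/INR for asymptomatic ALT/AST >3 to ≤5 × ULN with TBL ≤2 × ULN, so the protocol's own INR >1.5 stop could be missed in that band

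*Protocol*

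**What the plan says.** Section 9.3 of the protocol sorts liver abnormalities into laboratory triggers and liver events. The first category is "Liver laboratory triggers, which will require repeated assessments of the abnormal laboratory parameter"; the second calls for fuller work-up and the liver CRF pages.

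Table 9-1, "Liver Event and Laboratory Trigger Definitions", puts ALT/AST >3 to ≤5 × ULN among the triggers. It puts ALT or AST >3 × ULN combined with INR >1.5 among the events. For that combination Table 9-2 requires the site to "Discontinue the study drug immediately".

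For the trigger, the text of Section 9.3 asks for "Repeating the LFT within the next week to confirm elevation". The matching row of Table 9-2 (>3 to ≤5 × ULN, asymptomatic) adds "If elevation is confirmed, initiate close observation of the patient", and its follow-up column reads "Investigator discretion Monitor LFT within 1 to 4 weeks". The more severe rows differ: their follow-up column begins "ALT, AST, TBL, Alb, PT/INR, ALP and" and ends with γGT.

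On routine testing, footnote 12 to Table 8-1 says: "Routine clinical laboratory tests includes hematology, clinical chemistry (+ lipid profile), and NTproBNP". The hematology and chemistry lists in Section 8.4.4 contain no PT, INR or other coagulation test.

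**The concern.** The INR >1.5 rule begins at 3 × ULN, so a site can apply it only if it has an INR for each patient above that level. Most routes through Table 9-2 either name PT/INR or stop the drug for another reason. One route appears to do neither: no symptoms, ALT/AST >3 to ≤5 × ULN, and TBL ≤2 × ULN.

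A site that follows the written trigger steps exactly could keep such a patient on daily dosing although the patient already meets an immediate-stop criterion. What is at stake is individual safety. The efficacy analysis is not touched.

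**Working it through.** No sample-size or power arithmetic applies. The check is a row count of Table 9-2, followed by a trace of one patient through the visible text.

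**Step 1. Count the rows.**

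| Table 9-2 row | PT/INR named in follow-up | Unconditional immediate stop |
|---|---|---|
| Potential Hy's Law | yes | yes |
| ALT/AST >8 × ULN | yes | yes |
| ALT/AST >3 × ULN and INR >1.5 | yes | yes |
| ALT/AST >5 to ≤8 × ULN | yes | no |
| ALT/AST >3 × ULN with symptoms | yes | yes |
| ALT/AST >3 to ≤5 × ULN, asymptomatic | **no** | no |
| ALP >2 × ULN | no | no |
| TBL >2 × ULN | yes | no |
| TBL >1.5 to ≤2 × ULN | no | no |
| Jaundice | yes | yes |
| Other AE suggesting liver toxicity | no | no |

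Totals: 7 of 11 rows name PT/INR and 4 do not. Within the ALT/AST block, 4 of 5 name it, and the exception is the asymptomatic >3 to ≤5 × ULN row. Five rows carry an unconditional immediate stop, and one of those five depends on INR.

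**Step 2. Trace the patient.** Take ALT at 4 × ULN, TBL ≤2 × ULN, no symptoms, and an INR that is above 1.5 but not yet measured.

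- Routine laboratory tests (Table 8-1 footnote 12; Section 8.4.4): no coagulation test is listed, so no INR arrives by default.
- Incidental source: warfarin is prohibited (Section 5.3), so warfarin monitoring supplies no INR.
- Classification (Table 9-1): on the results in hand, a laboratory trigger.
- Trigger step (Section 9.3): repeat the LFT. The category description ties the repeat to the parameter that was abnormal, here ALT.
- Table 9-2 row: close observation if confirmed, then LFT monitoring. PT/INR is not named.
- INR >1.5 row: it names PT/INR for follow-up, which applies once INR is already known to be raised. It cannot find the case.
- Neighbouring rows: TBL between 1.5 and 2 × ULN, or ALP above 2 × ULN, does not help, because those rows name no PT/INR either.

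The trace ends without an order for INR.

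**Step 3. Mark the edges.** Above 5 × ULN, Table 9-2 names PT/INR. With the listed symptoms, or as a potential Hy's Law case, the drug is stopped anyway. The gap is confined to this one band.

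**Step 4. Compare with reflex tests the protocol does write.** Section 8.4.4 asks for bilirubin fractions when total bilirubin exceeds 1.5 × ULN, and for urine microscopy after certain positive dipstick results. There is no visible counterpart for INR after a raised transaminase.

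**The case against.** The strongest reply has three parts.

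First, the protocol does not leave the site without a prompt. Table 9-1 names INR at ALT/AST >3 × ULN, so a site separating a trigger from an event is reminded of it. Follow-up in this row is at the investigator's discretion, Section 7.1 obliges the investigator to stop treatment judged harmful, and Section 8.4.4 requires clinically relevant deviations to be discussed with the sponsor. This stands to the extent that a careful site may well order the test. A reader might infer that the stop would be missed in every such patient; the documents support only that it could be. Even so, a prompt is not an order, and Section 9.3 describes its liver process as standardized and obligatory. A mandatory stop should not depend on an optional test.

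Second, not all the relevant text is visible. LFT is expanded in the abbreviation list but never itemised. A block of Section 8.4.4 just before Urinalysis is redacted. NTproBNP appears in footnote 12 but not in the visible panels, so the visible lists are not complete. The Site Operations Manual is a separate document. Any of these could supply an INR rule. Two things weigh against it without settling it: Table 9-2 names PT/INR separately where it is wanted, and footnote 12 shows no coagulation test.

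Third, the case is uncommon: a raised INR with modest transaminases, TBL ≤2 × ULN, no symptoms and no warfarin, over 28 days of dosing. Confirming mild asymptomatic elevations before escalating is a coherent design. This limits the priority of the point but does not remove the mismatch between the stop rule and the tests ordered.

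**Conclusion.** The point holds in a limited form. For asymptomatic ALT/AST >3 to ≤5 × ULN with TBL ≤2 × ULN, no visible panel or laboratory-trigger step orders PT/INR, so one of the protocol's five unconditional immediate-stop criteria could go undetected in that band. This rests on the visible text, and on LFT not already including PT/INR through the laboratory panel, the redacted block or the Site Operations Manual.

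The documents give no rate for this band. With about 40 patients on active drug, the number affected is probably small.

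A reader might infer that the exposure can be measured by the doses taken while waiting up to a week for the repeat LFT. The documents do not support that. If the LFT carries no INR, its timing does not mark when the INR becomes known; if it does carry one, the gap closes. A trigger on a sample taken at the end of dosing also leaves no doses to withhold. No dose figure should be attached.

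This is a cheap safety improvement, not a flaw in the trial's conclusions.

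**What to change.** In the >3 to ≤5 × ULN row of Table 9-2, and in the laboratory-trigger bullet of Section 9.3, require PT/INR with the repeat draw for any ALT/AST above 3 × ULN. It should preferably be done within 48 hours, the interval Table 9-2 already sets for LFT repeats in the ALT/AST >5 to ≤8 × ULN, ALP >2 × ULN and TBL >2 × ULN rows, and no later than the repeat LFT. Apply the existing INR >1.5 stop to the result. If the Site Operations Manual or the laboratory's LFT panel already provides this, a cross-reference in Section 9.3 is enough.

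The test belongs on the redraw: nothing visible shows that a sample suitable for coagulation testing is collected at the routine visits.

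The cost is one line of wording in each of the two places, and one coagulation test per triggering patient, possibly with an earlier redraw. Purely as an assumption, if 1% to 5% of the 80 randomised patients reached ALT/AST >3 × ULN, that would be 0.01 × 80 = 0.8 to 0.05 × 80 = 4 tests, or about 1 to 4 across the trial. No routine testing is added.
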